8.4.2 Study-Level Stopping Criteria

Study enrollment is to be paused if any of the below criteria are met:

- If ≥ 3 subjects develop the same related Grade 4 (life-threatening) adverse event or laboratory abnormality;
- If ≥ 5 subjects develop the same related Grade 3 or 4 adverse event or laboratory abnormality;
- If ≥ 10 subjects develop any related Grade 3 or 4 adverse event or laboratory abnormality.

Following assessment by the Data Monitoring Committee (DMC, see [Section 10.9](#)), the DMC will determine whether to stop the study, amend the protocol, or continue the study per protocol.

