	
Investigator or designated person to be related to study drug. Treatment-emergent adverse events will be those with an onset after the date and time of first treatment.
 
Subjects who develop Grade 3 or 4 toxicities or SAEs are to be re-evaluated every 2 days, as feasible, until the toxicity returns to Grade ≤ 2 severity.
 
During assessment for adverse events, investigators and site staff are to elicit from the subject any signs or symptoms of mucositis or thrombocytopenia, e.g.:
 
• Ecchymosis/purpura/petechiae• Epistaxis• Hemoptysis• Hematuria• Gingival bleeding• Prolonged bleeding time from needle sticks, abrasions or lacerations• Hematemesis• Rectal bleeding• Blood in stool• Any other unusual bleeding noted by the subject or caregiver
Stopping Criteria	
Individual Criteria:
 
• Participants who develop a Grade 3 toxicity that is assessed by the investigator to be related to the study drug are to be permanently discontinued from study treatment.• Participants who develop a Grade 4 toxicity, regardless of relatedness to study drug, are to be permanently discontinued from study treatment. 
Study-Level Stopping Criteria:
 
Study enrollment is to be paused if any of the below criteria are met:
 
• If ≥ 3 subjects develop the same related Grade 4 (life-threatening) adverse event or laboratory abnormality;• If ≥ 5 subjects develop the same related Grade 3 or 4 adverse event or laboratory abnormality;• If ≥ 10 subjects develop any related Grade 3 or 4 adverse event or laboratory abnormality. 
All adverse events will be reviewed by the DMC during their reviews. Following assessment by the Data Monitoring Committee (DMC), the DMC will determine whether to stop the study, amend the protocol, or continue the study per protocol.

Statistical Analysis	
A separate, detailed statistical analysis plan (SAP) will be finalized prior to locking the database. All analyses of safety and efficacy for this study will be descriptive in nature and presented by group. Subject demographics and baseline characteristics will be summarized. Subject data listings will also be provided.
 
Summaries for quantitative variables will include the mean, median, quartiles,

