8.2.1 Safety/Tolerability

Safety/tolerability is assessed for each subject at each study visit. The *NIH Division of AIDS (DAIDS) Table for Grading the Severity of Adult and Pediatric Adverse Events, Corrected Version 2.1 (July 2017)* will be utilized for AE reporting. All appropriate treatment areas should have access to a copy of the criteria.

Adverse events (AEs) commonly observed in patients treated with brequinar are provided in the Investigator's Brochure (IB) and include thrombocytopenia, nausea, anemia, diarrhea, vomiting, leukopenia, stomatitis, rash, granulocytopenia, fatigue, and infection. In a study of 209 cancer subjects treated once-weekly (DuP 785-012, see Brequinar IB [5]), the deaths of three patients were attributed to study drug toxicity (two to hemorrhage, one following acute renal failure). Severe toxicities grades (Grades 3 to 4) which typically led to discontinuation in this study included hematologic toxicities (anemia, thrombocytopenia, leukopenia, granulocytopenia), digestive system toxicity (nausea, vomiting, stomatitis, others including gastric hemorrhage) and mucositis.

In three oncology studies with five consecutive days of intravenous (IV) brequinar dosing in 168 subjects (Study 785-001 [14], 785-003 [15], and 785-005 [16]) there were no toxic deaths. For subjects from these three studies who were treated with a daily dose of 100 mg or below (as will be dosed in CCB-CRISIS-02), AEs through 21 days showed that 2 of 39 subjects (5.1%) had a severe (Grades 3 or 4) AE related to study drug (1 subject each with hyperbilirubinemia and hyperglycemia), and no subjects discontinued from the study due to a study drug-related AE. The few study drug related AEs through 21 days at or below the 100 mg dose from these three studies included 2 subjects each with nausea, vomiting, and creatinine elevated and one subject each with thrombocytopenia and diarrhea. When only studies with oral dosing were considered at this dose level (Studies 785-022 [17], 785-031 [18], and 785-034 [19]), the study drug related AEs through 21 days (each observed in one subject only) included diarrhea, headache, nausea, pruritus, abdominal pain, anorexia, chest pain, dry mouth, fatigue, keratosis, stomatitis, and vomiting. See brequinar IB [5].

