8.7.4 Unblinding/Expectedness

Contact the Covance Medical Monitor if it is necessary to break the blind for this blinded study due to an adverse event (AE). Each site will be provided with a sealed envelope containing individual sealed envelopes for subject numbers assigned to that site. Each individual subject number sealed envelope will have the treatment (brequinar or placebo) randomly assigned to that subject number. Do not open the outer envelope or the individual sealed envelope unless it has been agreed with the Medical Monitor and the Sponsor that unblinding is necessary for that particular AE. Unblinding must be documented in the study records. Envelope seals are to be checked to ensure they remain intact during drug accountability monitoring.

If after a discussion with the Medical Monitor, the investigator or treating clinician believes the AE leading to unblinding to be related to the study drug, no further doses of drug should be administered to that subject.

Expectedness will be determined by establishing whether an adverse event is among those identified in the protocol and the brequinar IB or are commonly associated with COVID-19 or similar severe viral illnesses and their complications.

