If a death occurs during the SAE reporting period, the cause of death such as pneumonia, ARDS, or respiratory failure, is considered as the AE and the death is considered its outcome. Death should be considered an outcome, not an event. The event or condition leading to death should be recorded and reported as a single medical concept on the AE eCRF. Generally, only one such event should be reported. "Fatal" will be recorded as the outcome of this respective event; death due to an outcome of an AE will not be recorded as separate event. If the primary cause of death is disease progression, the cause of death should be clearly identified as COVID-19.

In cases of surgical or diagnostic procedures, the condition leading to the procedure is considered as the AE instead of the procedure itself. Each AE will be coded by the Sponsor from the verbatim text to a preferred term using a thesaurus based on the Medical Dictionary for Regulatory Activities (MedDRA). For example, record appendicitis, not appendectomy.

The following guidelines will be followed for the recording and reporting of adverse and serious adverse events.

1. The medical history section of the case report form will serve as the source document for baseline events.
 - a. Baseline events are any medical condition, symptom, or clinically significant lab abnormality present before the informed consent is signed.
 - i. If exact start date is unknown, month and year or year may be used as the start date of the baseline event.
2. Adverse events occurring after first dose are to be recorded in the eCRF using the AE form.
3. Serious adverse events will be reported to the local IRB according to institutional policy.

The *NIH Division of AIDS (DAIDS) Table for Grading the Severity of Adult and Pediatric Adverse Events, Corrected Version 2.1 (July 2017)* (<https://rsc.niaid.nih.gov/sites/default/files/daidsgradingcorrectedv21.pdf>) will be used for adverse event reporting.

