10.5 Serious Adverse Event (SAE) Reporting

The regulatory definition of an SAE is any untoward medical occurrence or effect that at any dose fulfills one or more of these criteria:

- results in death;
- is life threatening (at the time of the event);
- requires in-patient hospitalization or prolongation of existing hospitalization;
- results in persistent or significant disability / incapacity
- is a congenital anomaly / birth defect;
- or is an event considered medically serious by the Investigator.

Disability is defined as a substantial disruption of a person’s ability to conduct normal life functions.

A life-threatening adverse event is one that places the patient/subject, in the view of the Investigator, at immediate risk of death from the event as it occurred. It does not include an event that, had it occurred in a more severe form, might have caused death.

An unexpected adverse event is any adverse drug event, the nature or severity of which is not consistent with the applicable product information (e.g. IB for an unauthorized investigational product or summary of product characteristics for an authorized product).

Enter only one event as the reason for the SAE on the SAE form. Other non-serious events which did not directly result in the SAE should be detailed in the description section on the SAE form and listed separately as AEs if necessary. For fatal SAEs, report the cause of death as an SAE with a fatal outcome rather than reporting death as the SAE term.

Note that hospitalizations for the following reasons should not be reported as SAEs:

- Routine treatment or monitoring of COVID-19 infection, not associated with any deterioration in condition;
- Elective or pre-planned treatment for a pre-existing condition that is unrelated to the indication under study and has not worsened since signing the informed consent;
- Social reasons and respite care in the absence of any deterioration in the subject's general condition;
- Treatment on an emergency outpatient basis that does not result in hospital admission and involves an event not fulfilling any of the definitions of an SAE given above.

ANY SERIOUS ADVERSE EVENT MUST BE REPORTED IMMEDIATELY (WITHIN 24 HOURS) BY EMAIL TO THE SAE REPORTING EMAIL USING THE FORM PROVIDED. ENTER THE SUBJECT'S AVAILABLE INFORMATION INTO THE eCRF WITHIN 48 HOURS.

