10.6 Suspected Unexpected Serious Adverse Reactions (SUSARs)

Suspected, unexpected, serious adverse reactions (SUSARs) are SAEs that are both related to the study drug (Relationship = Related) and unexpected (not previously described in the investigator's brochure). All SUSARs will be reported in an expedited manner to the Sponsor or designee and IRB by the Investigators and to all relevant regulatory authorities by the Sponsor. Expectedness will be judged by the Covance Physician and site Investigator. It is critical that all SAEs are reported within the 24-hour guideline so that the expectedness determination can be made. SUSARs require immediate attention and expedited reporting to relevant regulatory authorities.

The Sponsor will ensure that all relevant information about **fatal or life-threatening** SUSARs are appropriately recorded and reported to the concerned Regulatory Authority and to the concerned

IRB(s) within seven (7) calendar days of the date of first report to Covance Patient Safety / Sponsor. Follow-up information will be communicated to the relevant Regulatory Authority within an additional eight calendar days.

All other SUSARs will be reported to the Regulatory Authority and to the IRB(s) concerned as soon as possible within a maximum of fifteen calendar days of first notification to Covance Patient Safety / Sponsor.

The Sponsor or designee will also inform all Investigators studying the investigational medicinal product about SUSARs and ensure that all IRBs have been notified.

For reported deaths of a subject, the Investigator shall supply the Sponsor and the IRB(s) with requested additional information on an expedited basis.

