10.8 Safety Monitoring for Hematologic Toxicities

Myelosuppression is a known effect of DHODH inhibition that is associated with prolonged exposure and high doses. To reduce the risk of this effect with brequinar in COVID-19 subjects, the extensive brequinar safety database with over 1,000 patients has been evaluated to select a dose level expected to be safe and well tolerated with regard to hematologic toxicity. In addition to enhancing safety by

selecting a relatively brief 5-day exposure and a low brequinar dose, all subjects in the clinical trial will be under the care of highly qualified medical personnel. Clinically significant out-of-range laboratory results will be reported as adverse events.

In addition to real time assessments by the treating clinical team, the Covance Medical Monitor will assess the available hematology data on a periodic basis to identify any pathologic trends or safety issues. Any apparent increase in the expected rate or severity of hematologic safety events will be discussed with the Principal Investigators and the Sponsor. In addition, the Data Monitoring Committee (DMC) will assess available hematology data on a periodic basis to independently assess any pathologic trends or safety issues. If the rate or severity of hematologic toxicities appears to be above the expected rate or the severity appears worse than that expected, the trial enrollment will be suspended and no further subjects will be treated while a comprehensive data review is conducted. Depending on the outcome of the safety review the study may be stopped, the design adjusted, or the study may continue as designed. Individual and Study stopping rules are provided in [Section 8.4](#).

Safety laboratory results are to be initially assessed in real time by the Principal Investigator or designated person. Any study drug-related clinically significant out-of-range laboratories or study drug-related adverse events will be followed as needed until resolution or stable.

The in-clinic assessments and telemedicine/phone call visits will specifically ask about possible hematologic toxicity including any evidence of the list below. Subjects will be provided with a list of the following events in lay terms and will be instructed to call the research team if any of these events occur.

- Ecchymosis/purpura/petechiae
- Epistaxis
- Hemoptysis
- Hematuria
- Gingival bleeding
- Prolonged bleeding time from needle sticks, abrasions or lacerations
- Hematemesis

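### The mandatory enrollment-pause rules have no fatal-outcome trigger, so one or two related non-hematologic deaths would not by themselves compel a pause under the protocol as written

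*Protocol*

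**What the plan says.** **Compulsory pause.** Protocol v5.0 Section 8.4.2 pauses enrollment if any one of three counts is reached:

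- three or more "subjects develop the same related Grade 4 (life-threatening) adverse event or laboratory abnormality";
- five or more with the same related Grade 3 or 4 event;
- ten or more with any related Grade 3 or 4 event.

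The synopsis has the same counts, including the "related Grade 4 (life-threatening) adverse event or laboratory abnormality" bullet, and adds only that the DMC reviews all adverse events. Neither place mentions a fatal outcome.

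**How a death is recorded.** Section 10: "Death should be considered an outcome, not an event". Fatal is entered as the outcome of the causal event.

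**The other compulsory suspension.** Section 10.8 suspends enrollment "If the rate or severity of hematologic toxicities appears to be above the expected rate" or if severity looks worse than expected. It is confined to hematologic toxicity.

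**Other provisions.**

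- Section 10.5: "ANY SERIOUS ADVERSE EVENT MUST BE REPORTED IMMEDIATELY (WITHIN 24 HOURS".
- Section 10.6: fatal or life-threatening SUSARs go to the regulator and IRBs "within seven (7) calendar days of the date of first report to Covance Patient Safety / Sponsor".
- Synopsis and Section 10.9.1: the DMC meets periodically, with looks after 20 and 40 subjects complete Day 8. The synopsis calls these a minimum.
- Section 9.8: termination for safety is discretionary.
- Section 10.9 and SAP 7.8: the DMC's specific responsibilities are in a separate charter.

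**Prior deaths.** Section 8.2.1 attributes three deaths among 209 once-weekly cancer subjects to drug toxicity: "two to hemorrhage, one following acute renal failure". It reports no toxic deaths among 168 subjects in the three five-day intravenous studies, of whom 39 received 100 mg a day or less.

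**The concern.** The ordering is odd. Three subjects who survive the same related life-threatening event stop enrollment, but one subject who dies of a related renal, hepatic or other non-hematologic toxicity does not. What is at stake is the interval after such a death, when sites may keep enrolling and dosing in full compliance with the protocol until someone uses discretion.

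The protocol does not treat non-hematologic toxicity as remote. Section 8.2.1 warns that brequinar-related events may be fatal. Among the 39 five-day subjects at 100 mg or less it lists related creatinine elevation in two and one severe related hyperbilirubinemia.

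**Working it through.** The plan gives no operating characteristic for its stopping rules, so there is no figure to reproduce.

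**1. Apply the rules as written.** The protocol does not say whether a fatal event counts as Grade 4. Take the reading most favorable to the protocol, that it does. Pause = (same Grade 4 ≥ 3) or (same Grade 3/4 ≥ 5) or (any Grade 3/4 ≥ 10).

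| Related non-hematologic deaths, nothing else counted | All the same event | All different events |
|---|---|---|
| 1 | no pause | no pause |
| 2 | no pause | no pause |
| 3 | pause | no pause |
| 4 or 5 | pause | no pause |

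A fatal event could complete a count begun by non-fatal events, but one or two deaths alone never reach a threshold. If fatal events do not count as Grade 4, they add nothing to the counts, so one or two deaths again force no pause.

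**2. Choose rates.** No applicable rate is given, so r is an assumption: 0.25%, 0.48% and 1%. The middle value is 1/209 = 0.478%, the renal death under a different regimen and disease (exact 95% CI 0.01% to 2.6%). The five-day data give 0/168 (exact 95% upper limit 2.2%) and 0/39 at 100 mg or less (upper limit 9.0%). These are compatible with all three rates and with a rate near zero.

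**3. Related non-hematologic deaths among n = 50 brequinar subjects** (binomial).

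- P(≥1) = 1 − (1 − r)^50
- P(≥2) = P(≥1) − 50·r·(1 − r)^49
- P(≥3) is the binomial tail from 3

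| r | P(≥1): a pause on any such death fires | P(≥2): a second such death occurs | P(≥3): most the current rule could fire on these deaths alone |
|---|---|---|---|
| 0.25% | 0.118 | 0.007 | 0.0003 |
| 0.478% | 0.213 | 0.024 | 0.0018 |
| 1% | 0.395 | 0.089 | 0.0138 |

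For r = 1%: 1 − 0.99^50 = 0.395, and 0.395 − 50 × 0.01 × 0.99^49 = 0.395 − 0.306 = 0.089. The last column assumes every death is the same event and counts as Grade 4.

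**4. Unnecessary pauses.** Section 10.3 counts Possible as drug related, so a COVID-19 death in either arm could trigger the new rule. With any-cause mortality d and share f of deaths called related, both assumed, the chance of at least one such pause in 100 subjects is 1 − (1 − d·f)^100.

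| f | d = 0.5% | d = 1% | d = 2% |
|---|---|---|---|
| 10% | 5% | 10% | 18% |
| 25% | 12% | 22% | 39% |
| 50% | 22% | 39% | 63% |

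**The case against.** The case against a change has real weight.

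- **The charter is not available.** It may already require a pause or an ad hoc review after a related death. A reader might infer that the trial has no such rule. The documents support only the narrower statement that Section 8.4.2 neither contains nor cites one.
- **A pause cannot prevent the death that triggers it.** A reader might take 12%, 21% and 39% as harm averted. They measure how often the trigger would fire. P(≥2) is the ceiling on averting a second such death, and even that is generous: some subjects would already be dosed, and the sponsor or DMC may act anyway. Non-fatal harm is outside this figure.
- **False pauses may be about as frequent as true ones.** At 1% mortality and 25% attribution the chance is 22%, against 21% at the middle rate. This stands as a cost, though the DMC can lift each pause.
- **Upstream safeguards exist.** Section 7.3 excludes creatinine clearance below 30 mL/min and raised liver tests. Chemistry is drawn at Screening and Days 1, 8 and 15, with review within 48 hours of results. Individual treatment stops for related Grade 3 or any Grade 4 toxicity, and adverse events are assessed on each of Days 1 to 8. These make such a death less likely but do not settle what happens to enrollment after one.

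Two further inferences should be resisted. One is that subjects enrolled after the 40-subject look go unreviewed. The synopsis makes the two looks a minimum within periodic meetings. The other is that a related renal death would be classed as expected and so escape seven-day reporting. Section 8.7.4 could be read that way: "Expectedness will be determined by establishing whether an adverse event is among those identified in the protocol and the brequinar IB", or is commonly associated with COVID-19. But Sections 10.5 and 10.6 define unexpected against the product information or investigator's brochure alone. Section 10.6 also requires expedited supply of requested information on reported deaths without regard to expectedness. In any case, expectedness does not decide whether Section 8.4.2 compels a pause.

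**Conclusion.** The gap is established by the text and depends on no assumed rate: one or two related non-hematologic deaths meet no compulsory pause criterion in the protocol. Reporting, DMC advice and discretionary termination remain open, but none is a mandatory pause. Hematologic deaths are outside the point, because Section 10.8 would suspend enrollment if the toxicity appeared worse than expected.

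The size is uncertain. On the assumed rates, the measurable gain is at most a 0.7% to 8.9% chance that a second such death was there to be averted, and a rate near zero also fits the five-day data. The change is worth making because it is cheap and puts the rules in a sensible order, not because a large benefit has been shown. Confidence is medium, mainly because the charter is not available.

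**What to change.** Add one bullet to Section 8.4.2 and to the synopsis study-level criteria: *If any subject has a related adverse event (Section 10.3) with a fatal outcome, enrollment is paused pending DMC review.* Leave the counts of 3, 5 and 10 and Section 10.8 unchanged. The bullet overlaps Section 10.8 for hematologic deaths, which does no harm. If the DMC charter already requires this pause, cite it in Section 8.4.2 instead.

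No new data are needed: fatal outcome and relatedness are already recorded, and SAP 7.7.2 already tabulates drug-related events leading to death. The costs are a substantial amendment with IRB approval before implementation (Section 9.3) at about 15 sites, and a 5% to 63% chance of at least one unnecessary pause across the assumed scenarios. Section 8.4.2 sets no limit on the length of a pause, but the DMC assessment it already prescribes can end one.

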8.5 Concomitant Medication/Treatment

Record the name, dose, start/stop date, indication for use, route, and whether ongoing or stopped for medications/treatments taken within two weeks prior to study entry as well as any medications taken during the study are to be recorded. Prohibited medications are identified in [Section 8.8](#).

